We have several secondary hypotheses: a) decolonization of oropharyngeal *S. aureus* colonization with 0.12% CHG will be sustained at 28 days; b) recolonization of the oropharynx will come from isolates that colonize patients nose and not from development of antimicrobial resistance, including the emergence of CHG-resistant *S. aureus* strains that contain the *qac A/B* genes; and c) predictors of failure to decolonize with CHG will include poor treatment adherence, nasal *S. aureus* colonization, and younger age.

If our primary hypothesis is correct, findings will form the foundation for a larger, randomized, prospective, multi-center, placebo-controlled clinical trial comparing skin, nasal, and oropharyngeal decolonization vs. standard of care decolonization regimen for the prevention of recurrent *S. aureus* skin infections. If oral CHG rinse is unable to decolonize the oropharynx, then other more aggressive oropharyngeal *S. aureus* colonization eradication strategies in children will need to be tested.

B. Specific Aim(s) of the Project

1) Determine the efficacy of oropharyngeal decolonization among children with a history of CA-MRSA, CA-*S. aureus* or skin and soft tissue infection (SSTI). To determine if oropharyngeal *S. aureus* colonization can be eradicated, we will perform a randomized, double blind placebo-controlled controlled clinical trial comparing 0.12% oral chlorhexidine (CHG) oral rinse to placebo among children age 5-17 with *S. aureus* oropharyngeal colonization. We hypothesize that 0.12% CHG rinse will reduce oral *S. aureus* colonization better than placebo treatment. Our findings will provide “proof of principle” data on the ability of oral antiseptics to eradicate oropharyngeal *S. aureus* colonization in children.

2) Assess the safety, tolerability, and compliance of oropharyngeal decolonization among children and their caregivers. Using a structured instrument, we will survey trial participants and their parents/guardians on side effects, tolerability, and adherence of the 0.12% oral CHG rinse and placebo. Findings will serve as a counterpoint to any benefits derived from oral decolonization.

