Subjects will also be swabbed for *S. aureus* and MRSA colonization at the anterior nares and oropharynx. Testing will be performed using two methods: direct microbiology cultures and rapid molecular testing. Microbiologic cultures will be performed by culturing swabs from sites taken to identify *S. aureus* and MRSA carriage will be transported to the research microbiology laboratory at LA BioMed at Harbor-UCLA and plated within 24 hours of collection. Swabs will be processed for *S. aureus* using blood agar and CHROMagar plates for rapid identification of *S. aureus* and MRSA. All *S. aureus* and MRSA isolates will be banked for pulse-field typing, determination of SCCmec type, and presence of the PVL locus (*lukF-PV* and *lukS-PV*). Rapid molecular testing will be performed using the GeneXpert MRSA/SA platform, which is currently available at our site.

Upon confirmation of eligibility, the study coordinators will call the pharmacy to randomize the participant and obtain the oral rinse. The randomization assignment list will be generated in advance by pharmacy. Randomization procedures by an assignment list will be prepared by a computer method. To ensure adequate balance of subjects between the CHG and placebo groups, treatment allocation will be assigned using a random number generation with randomization of blocks of four subjects each. The randomization list will be kept by the pharmacy and treatment allocation randomization will not be shared with either the study staff or patients. The research pharmacists will dispense the appropriate oral rinse to the participant and their parent/guardian. Placebo will be created using the inert vehicles components of CHG, as has been done previously.⁸⁹ Participants and their parent/guardian will be given detailed instructions on the use of the oral rinse both verbally and in a handout in either English or Spanish as preferred by the participant and their parent/guardian.

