Using an alpha of 0.05 and expected cure rates of 50% and 10% in the CHG and placebo arms respectively, 54 subjects (27 per group) would be needed for 85% power to detect a 40% absolute difference in cure ($p<0.05$) between groups. Correcting for a 10% attrition rate, 60 enrolled subjects would be needed. To identify 60 subjects with oropharyngeal colonization, and assuming 33% of patients who are high risk for *S. aureus* colonization will have oropharyngeal colonization, 240 subjects will need to be screened to obtain 80 patients that are oropharyngeally colonized with *S. aureus*. Of these, 75% (n=60) will have *S. aureus* detected by the GeneXpert rapid test and will undergo randomization.

Data Analyses and Data and Safety Monitoring

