The decolonization rate will be calculated as the number of subjects who remain decolonized divided by the number of subjects, and treatment group differences as differences in these rates. The precision of estimated rates and rate differences will be expressed with two-sided confidence intervals calculated as asymptotically normal approximations to binomial or differences in binomial random variables. The level of confidence for these intervals will be 95%. Statistical significance for differences between treatment groups in cure rates will be determined from Fisher’s exact tests. The level of significance for these tests is 0.05. Factors associated with failure of decolonization in the CHG treatment group will also be examined. Based on prior investigations of *S. aureus* colonization from our group and others, these will include demographics (age, gender, race/ethnicity), co-morbidities, measures of hygiene, number of prior skin infections in the prior year, antibiotic use in the prior year, household history of skin infection, adverse effects and tolerability (see Aim 2, below), and treatment adherence. Additionally, we will examine pathogen level predictors of decolonization failure, based on molecular characterization of baseline isolates (see Aim 3). These factors will include baseline colonization with USA300 strain, presence of qac A/B gene, presence of nasal colonization, presence of nasal colonization with a strain identical to the oropharyngeal colonizing strain, and presence of nasal colonization with a strain differing from the oropharyngeal colonizing strain. Associations will be examined using Chi-squared, Fisher Exact test, Wilcoxon rank sum test, or T-test, as appropriate. Small sample size will preclude multivariable analyses of factors independently associated with failure to decolonize. This analysis will be key to identifying factors associated with decolonization failures. Identification of mutable factors associated with decolonization failure will be key towards improving the success of future efforts at oropharyngeal eradication of *S. aureus*. Identification of non-mutable factors will be key towards identifying groups that may need more intense intervention and or education.

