All reported adverse events (regardless of treatment-emergent or not) will be included in a by-subject adverse event listing. Only treatment-emergent adverse events will be included in summary tables. The number of subjects (incidence) of treatment-emergent adverse events will be presented as well as the frequency of all adverse events reported.

Summary tables of adverse events will include the following:

- Summary of adverse events by severity and relationship
- Summary of related adverse events
- Summary of Serious adverse events
- A listing of any on-study pregnancies

Percentages of subjects who reported adverse events will each be compared separately among each group using Chi-Square or Fisher Exact tests, as appropriate.

Aim 3: Determine the *S. aureus* genetic backgrounds associated with breakthrough oropharyngeal colonization.

Advances in sequencing technologies and the availability of large computing power and bioinformatics have allowed WGS to become the method of choice to characterize emerging phenotypes.⁷² WGS also allows examination of the relationship between presence of the *qac A/B* gene in *S. aureus* at baseline and treatment response. WGS allows detection of this plasmid-based resistance gene for comparative analysis among a subset of *S. aureus* isolates from our population, as described below.

We will molecularly characterize all baseline *S. aureus* isolates and “breakthrough” (failure) isolates using whole genome sequencing (WGS) for identification of breakthrough *S. aureus* isolates. We will compare breakthrough isolates with baseline nasal and oropharyngeal isolates to determine if breakthrough isolates represent either: a) recolonization with the original oropharyngeal isolate, b) recolonization with the baseline nasal isolate, or c) acquisition of a new *S. aureus* strain. Additionally, we will investigate whether *S. aureus* associated with treatment failures have acquired or possess the *qac A/B* gene.

Sample Size

Data Analyses

WGS will be done in the laboratory of [name] (see Letter of Support), using established techniques.^{92,93} [name] lab has ample experience performing WGS on *S. aureus* and other bacterial pathogens.⁹²⁻⁹⁴ [name] lab will also supply analytic support to assist with interpretation of findings.

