WGS sequencing will addresses several hypothesis in those subjects randomized to CHG oral rinses, specifically: a) strains that are found in the oropharynx at end of treatment (Day 7) will be identical genetically to those at baseline and not represent acquisition of new *S. aureus* strain; b) recolonizing *S. aureus* strains at Day 28 among subjects successfully eradicated at Day 7 will represent (re)colonization with the original isolate that colonized the nasopharynx from the same individual (if present at baseline) or a new *S. aureus* strain not present at baseline and; c) nasal isolates found at baseline and follow up will be identical to synchronously identified oropharyngeal *S. aureus* isolates.

Based on data in older adults,¹⁹ we estimate that of the 30 subjects randomized to the CHG arm, 50% will be decolonized, leaving 15 subjects who will be *S. aureus* positive at the oropharynx at the end of treatment. Based on data of recolonization after decolonization in which recolonization can occur after the decolonization regimen is completed,¹⁰ we estimate that a 10% increase in colonization will be seen at Day 28, i.e., 18 subjects will be oropharyngeally colonized with *S. aureus* at Day 28. Thus, we anticipate we will have results in 33 pairs of oropharynx isolates (15 between baseline and Day 7, and 18 between baseline and Day 28, for a total of 66 isolates total). Additionally we will conduct whole genome sequencing on baseline nasal *S. aureus* isolates associated with the subsequent oropharynx isolates identified at Day 7 and/or Day 28. Based on previous data suggesting that ~45% of those colonized at the oropharynx will be colonized at the anterior nares,^{18,46,95} we estimate an additional 30 (45% x 66) nasal *S. aureus* isolates from baseline and follow-up will be present synchronously with oropharyngeal isolates.

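### Aim 2 compares adverse events between arms by significance test alone, with no risk difference or interval, so at about 30 per arm a non-significant result on a less common event leaves a large CHG excess unexcluded.

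*Combined protocol and SAP*

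**What the plan says.** Aim 2 covers safety, tolerability and compliance. Under Specific Aim(s) of the Project its purpose is stated as "Findings will serve as a counterpoint to any benefits derived from oral decolonization".

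The Data Analyses text under Aim 2 defines treatment-emergent events. It plans incidence, frequency, severity, relationship and serious-event summaries, and then gives the between-arm comparison: "Percentages of subjects who reported adverse events will each be compared separately among each group using Chi-Square or Fisher Exact tests, as appropriate". It names no effect measure, no interval and no rule for choosing between the two tests.

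Eradication is treated differently. Under Data Analyses and Data and Safety Monitoring (Aim 1) the plan says "The precision of estimated rates and rate differences will be expressed with two-sided confidence intervals", at the 95% level, with Fisher's exact test alongside. That sentence sits in the paragraph on the decolonization rate, and nothing extends it to adverse events.

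The trial is sized on eradication only. The Power and Sample Size section assumes that half of the CHG children and a tenth of the placebo children are cured, and concludes that "54 subjects (27 per group) would be needed for 85% power to detect a 40% absolute difference in cure". No power is stated for harms. The Human Subjects section names staining, calculus formation and altered taste as known effects of the rinse, without frequencies.

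**The concern.** Benefit will be reported as a difference with its precision. The harms meant to balance it will be compared by a test result. In a trial of 60 children, a test that misses 0.05 is weak evidence that an uncommon effect is no more frequent on CHG, and without an interval nothing in the planned output shows how large an excess the data still allow.

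The results are meant to support a larger trial of decolonization in children. A safety statement that rests on non-significance could carry forward an excess of 20 to 30 points or more that this trial was unable to exclude.

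**Working it through.** **Inputs from the documents**
- Power and Sample Size: cure 50% vs 10%, alpha 0.05, 85% power, 27 per group; "Correcting for a 10% attrition rate, 60 enrolled subjects would be needed".
- Baseline visit: "treatment allocation will be assigned using a random number generation with randomization of blocks of four subjects each", taken here as 1:1.
- Aim 3: "we estimate that of the 30 subjects randomized to the CHG arm, 50% will be decolonized".

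**Assumptions.** Adverse-event tests are two-sided at 0.05, because the Aim 2 section restates no level. Event rates are illustrative, because the documents give none.

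**Step 1: reproduce the plan's own figure.** With pooled rate 0.30, the uncorrected size per arm is

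n = [1.960 × √(2 × 0.30 × 0.70) + 1.036 × √(0.50 × 0.50 + 0.10 × 0.90)]² / 0.40² = 21.96.

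With the continuity correction, n′ = (n/4) × [1 + √(1 + 4/(n × 0.40))]² = 26.73, so 27 per arm and 54 in all. Then 54/0.90 = 60 randomized, or 30 per arm. The stated figures reproduce, and they concern a 40-point difference in eradication only.

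**Step 2: what a non-significant adverse-event table leaves open.** The Newcombe interval combines the Wilson limits (l, u) of each arm:

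lower = d − √[(p₁ − l₁)² + (u₂ − p₂)²]; upper = d + √[(u₁ − p₁)² + (p₂ − l₂)²].

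Take 5/30 vs 1/30. The Wilson limits are 7.3% to 33.6% and 0.6% to 16.7%, and d = 13.3 points.
- Lower = 13.3 − √(9.3² + 13.3²) = −2.9.
- Upper = 13.3 + √(16.9² + 2.7²) = +30.5.

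| CHG vs placebo events (30 per arm) | Difference, points | 95% Newcombe interval | Fisher p |
|---|---|---|---|
| 3 vs 1 | +6.7 | −8.2 to +22.5 | 0.61 |
| 5 vs 1 | +13.3 | −2.9 to +30.5 | 0.19 |
| 6 vs 2 | +13.3 | −4.7 to +31.3 | 0.25 |
| 9 vs 3 | +20.0 | −0.5 to +39.0 | 0.10 |

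With no events in 30 children, the exact two-sided 95% upper limit is 1 − 0.025^(1/30) = 11.6%.

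**Step 3: power of the planned test.** Each figure sums the joint binomial probabilities over every table with p ≤ 0.05, at 30 per arm.

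| Assumed CHG vs placebo rate | Fisher | Uncorrected chi-square |
|---|---|---|
| 15% vs 5% | 9% | 26% |
| 20% vs 5% | 24% | 45% |
| 30% vs 10% | 37% | 50% |
| 40% vs 10% | 71% | 80% |
| 60% vs 20% | 85% | 91% |

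**Step 4: does the choice of test matter?** At 5 vs 0, Fisher gives p=0.052 and uncorrected chi-square p=0.020; the Newcombe interval is 2.0 to 33.6 points. At 7 vs 1 the p-values are 0.052 and 0.023, and the interval is 2.4 to 37.8. The same data can fall on either side of 0.05.

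**The case against.** The best defence is that the plan reports far more than p-values. Incidence, frequency, severity, relationship and serious-event summaries are all planned, and the test itself compares percentages. This stands. A reader might infer that harms are reported by p-value only, or cannot be weighed against benefit, and the documents support neither. A crude difference can be had by subtracting the percentages. What is not planned is its precision.

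A reader might also infer that a several-fold CHG excess will usually be missed. That depends on rates the documents do not give, and it fails for commoner events: Fisher power is 71% for 40% vs 10% and 85% for 60% vs 20%. The plan also allows chi-square. If that is used whenever all expected counts are at least 5, which is one reading of the wording, power at 30% vs 10% is about 47% rather than 37%.

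Tables such as 5 vs 0 and 7 vs 1 look like striking examples but are poor ones. Their intervals exclude zero, so they show that Fisher is conservative, not that the data are inconclusive.

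Finally, the plan nowhere says that non-significance will be read as equal safety, and intervals add no power. Both points are true. The gap is that nothing planned guards against that reading.

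**Conclusion.** The point holds as a limited, correctable gap in the Aim 2 analysis. The only between-arm analysis of adverse events is a test, while eradication gets a difference and an interval.

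Its size depends on how common the event is. For placebo rates of 5% to 10%, a three-fold CHG excess has Fisher power of 9% to 37% at 30 per arm, and non-significant tables such as 5 vs 1 or 9 vs 3 leave excesses of 30 to 39 points unexcluded. For commoner events with large excesses the planned test performs reasonably.

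This rests on 30 analysed per arm, 1:1 allocation, two-sided tests at 0.05 and assumed event rates. With 27 per arm, Fisher power is lower still: 7% for 15% vs 5% and 31% for 30% vs 10%. The eradication analysis is unaffected.

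**What to change.** In the Aim 2 data analysis section:

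- Keep the planned incidence, frequency, severity, relationship and serious-event tables.
- Make the main between-arm summary the risk difference (CHG minus placebo) with a 95% Newcombe or other score-type interval. Give it for any treatment-emergent event and separately for staining, calculus formation and taste change.
- Do not carry over the normal approximation from the Aim 1 section. It is unreliable at small counts and collapses to zero width at 0 vs 0.
- Where an arm has no events, give the exact upper limit for its rate (11.6% for 0/30).
- Treat any test as secondary and say so in advance, because Fisher and the interval can disagree in borderline tables.
- Base the safety statement on the upper limit of the interval, and state that non-significance is not evidence of equal safety.

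The cost is one table column and a few sentences of SAP text, with no new data. The downside is that the intervals will be wide, which is an accurate picture of what 60 children can show.

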The body site of greatest *S. aureus* colonization has traditionally been believed to be the anterior nares.^{40,41} *S. aureus* has been known to colonize the axilla, perineum, rectum, vagina, and the throat (oropharynx).⁴²⁻⁴⁵ However, only recently have data regarding the importance and scale of non-nasal colonization been appreciated.⁴²⁻⁴⁵ An investigation conducted by our group in an area of high MRSA endemicity found that among persons with *S. aureus* SSTIs cultured at the anterior nares, oropharynx, and inguinal region, *S. aureus* colonized 40% (137/350) and 50% (405/812) of their household contacts.¹⁸ A nares-only survey would have missed 48% of *S. aureus* and 51% of MRSA colonized persons.¹⁸ Among the subset of patients with CA-MRSA infection, the proportion of oropharyngeal-only colonization was 12%, suggesting nasal-only screening for *S. aureus* colonization misses a sizable proportion of colonized patients with community onset SSTI. In fact oropharyngeal colonization was more prevalent than nasal colonization (26.0% vs. 24.0%) in our cohort of >1000 persons.¹⁸ Investigations of patients with acute skin infections and other populations at high risk for *S. aureus* infection by our group and others have demonstrated the prevalence of *S. aureus* oropharyngeal colonization are similar or exceed that of nasal colonization.^{17,43,44,46-49}

The failure of nares plus body decolonization at decolonizing patients and preventing recurrent *S. aureus* infections is disappointing. However, as outlined above, major efforts to prevent infection have employed mupirocin plus CHG (or bleach).^{8,16} Both nasal and body decolonization are well-established methods to decrease *S. aureus* in hospitalized patients.⁵⁰⁻⁵³ However, data on the efficacy of oral CHG rinses to eliminate oropharyngeal *S. aureus* colonization are extremely limited. Those few data that exist are from adults, largely elderly adults;¹⁹ thus the applicability of these limited data to children is unclear. **To truly perform studies of comprehensive *S. aureus* decolonization, oropharyngeal *S. aureus* colonization must be addressed therapeutically. However, there are few data on the efficacy of CHG at oropharyngeal *S. aureus* eradication and none in children.** If CHG is found to be effective in children, strategies that incorporate oropharyngeal decolonization as part of a more global eradication strategy may be critical for *S. aureus* SSTI prevention.

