In total 96 isolates will undergo whole genome analysis to address the hypotheses outlined above. Specifically, we will examine if decolonization failure of the oropharynx is due to any of the following: 1) a new and distinct *S. aureus* strain; 2) an isolate found at the nares at baseline; 3) an isolate found in the oropharynx at baseline; or 4) an identical strain from baseline but that has acquired with new resistance genes to CHG, specifically *qac A/B*. WGS typing of nasopharyngeal *S. aureus* isolates also allows us to determine if “breakthrough” oropharyngeal strains at Day 7 and/or 28 arise from endogenous or exogenous sources. Given that oropharyngeal and nasal isolates taken from the same person at the same time, are not always genetically identical,¹⁸ one cannot assume that baseline strains will be concordant. Finally testing of nasal oropharyngeal and nasal *S. aureus* at baseline and the Day 7 and 28 follow up visits, can assist in determination if resistance genes to CHG, specifically *qac A/B*, emerged after treatment in non-oropharyngeal, specifically nares sites, as it is known that antimicrobial therapy is associated with collateral damage among strains not specifically targeted by that treatment.³⁷ I.e., oral CHG may result in the emergence of *qac A/B* containing *S. aureus* strain in the nares. Analytically, the above analyses will be descriptive thus there are no power calculations for this aim.

Limitations

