This investigation is limited as it is a single center study. However, our center serves a ethnically and socioeconomically diverse population and findings from our investigations have been comparable to similar investigations in other populations.^{18,96,97} Our intervention is also singular in decolonization efforts (oropharynx only). However, no investigation has looked at the effect of *S. aureus* eradication on the oropharynx in children, so the addition of other decolonizing agents would prevent us from determining the efficacy of CHG oral rinse. Additionally, our trial is a “proof of principle” study that is required prior to a more comprehensive trial on *S. aureus* decolonization as a means for SSTI prevention. Finally, we are not performing WGS typing on all colonizing *S. aureus* isolates at all study time points, as it is known that *S. aureus* can colonize not only the nares and oropharynx, but the axilla, inguinal fold, perirectal area, vagina, and areas of skin that have lost integrity.^{42,47,98,99} However, the extra cost of testing these sites for possible sources of *S. aureus* that can later recolonize the oropharynx would be extremely expensive. Thus we chose just to perform testing in sites in which *S. aureus* is most commonly found (nares, oropharynx).

Future Directions

Investigation on prevention of recurrent *S. aureus* SSTI have been extremely disappointing, suggesting more comprehensive decolonization regimens need to be developed, especially those that focus on sites of colonization not previously targeted in clinical trials. Our investigation will be the first study to examine the efficacy of CHG to eradicate *S. aureus* from the oropharynx of children. [name] and his team provide ample experience in the area of MRSA infection and colonization, infectious disease expertise, clinical trials, and pediatrics. Besides the aims addressed for this investigation, our team is poised to address future aims related to *S. aureus* decolonization efforts and SSTI recurrences by generating information on the efficacy of CHG. In summary, the results of this investigation will provide the critical foundation for the development of future clinical trials. Data generated from our investigation will further investigative work on prevention of recurrent *S. aureus* SSTIs, which remain an extremely common and vexing clinical problem for clinicians, and more importantly, patients.

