All subjects who have consented will have the rapid *S. aureus* test performed with results shared with the subject's parent/guardian, the subject, and the clinician, if approved by the parent/guardian. Study staff will educate and the subject's parent/guardian, and subject (if of sufficient age), the clinical significance of the results, either positive or negative. More specifically, they will be educated that currently testing for *S. aureus* oropharyngeal colonization is considered experimental and that if the test is positive, the clinical significance is unclear. They will also be educated that tens of millions, perhaps over 100 million Americans are colonized in the throat with *S. aureus*, and the vast majority do not suffer consequences of having this bacteria live in the throat. Upon request, subjects will be provided with a written copy of their results as well as a written description of the clinical significance of oropharyngeal colonization that they can share with their provider, if they wish.

Subjects with a positive screening test will undergo 3 study visits total: baseline/enrollment visit (Visit 1), Day 7 (Visit 2), and Day 28 (Visit 3). Consenting subjects will have their anterior nares and oropharynx swabbed at Visits 1, 2, and 3. A survey will be administered at the initial visit and a follow-up survey will be administered at Visits 2, and 3. The survey administered at Visit 1 will collect information about demographics, medical history, and behavioral risk factors for skin and soft tissue infection and colonization. Subjects will be randomized to 0.12% CHG oral rinse or placebo use for 7 days. All subjects will receive educational materials regarding *S. aureus* and skin infections and their prevention. Those randomized to the intervention will receive additional verbal and written information on use of CHG oral rinse. The survey administered at Visit 2 will collect information about the adherence, tolerability, and adverse events during the intervention period. The survey administered at Visit 3 will collect information about (late) adverse events, changes in household dynamics and individual behavior (e.g., hygiene) that may affect results of Visit 3 nasal and oropharyngeal colonization studies.

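### Aim 3 labels a breakthrough strain that matches neither the baseline nasal nor the baseline throat isolate as newly acquired, but two-site sampling cannot show that it came from outside the child

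*Combined protocol and SAP*

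**What the plan says.** All references are to the combined protocol and SAP.

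- **Aim 3, opening text.** The comparison rule is "We will compare breakthrough isolates with baseline nasal and oropharyngeal isolates to determine if breakthrough isolates represent either" one of three things: the original throat isolate, the baseline nasal isolate, or "acquisition of a new *S. aureus* strain".
- **Aim 3, Data Analyses.** Two of the hypotheses use the same division. Under (a), Day 7 throat strains are expected to be the baseline strains rather than newly acquired ones. Under (b), Day 28 strains in children cleared at Day 7 are expected to be either the child's baseline nasal strain or a strain that was absent at baseline. The list of explanations for failure then gives a new and distinct strain as item 1, followed by "2) an isolate found at the nares at baseline; 3) an isolate found in the oropharynx at baseline", and item 4 covers a baseline strain that has gained *qac A/B*. The text goes on to say, without qualification, that typing allows the team to determine if breakthrough "oropharyngeal strains at Day 7 and/or 28 arise from endogenous or exogenous sources".
- **Human Subjects section.** The sampling is "Consenting subjects will have their anterior nares and oropharynx swabbed at Visits 1, 2, and 3". No other site is listed.
- **Limitations.** *S. aureus* is said to colonize "not only the nares and oropharynx, but the axilla, inguinal fold, perirectal area, vagina, and areas of skin that have lost integrity". These sites are described as possible sources of later throat recolonization, and they are left untested on grounds of cost.

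**The concern.** The classification has no place for a strain carried elsewhere on the child's own body, and none for an undetermined source. A breakthrough isolate that matches neither baseline isolate becomes new by default, and the endogenous/exogenous sentence invites the reader to take new as exogenous. What the data can support is narrower: the strain was not detected at baseline in two sites.

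This touches a stated purpose of the sequencing. The Scientific Abstract says it will separate strains the child already carried from newly acquired ones. Under the present rule, self-reseeding from unsampled skin by a different strain would count as support for hypothesis (b) and as evidence against hypothesis (a), although nothing would have been acquired from outside.

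**Working it through.** **Step 1. Reproduce the plan's isolate count (Aim 3, Data Analyses).**

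- Chlorhexidine arm: 30 children, 50% decolonized, so 30 × 0.5 = 15 positive at Day 7.
- Day 28: a rise of 10% of 30, so 15 + 3 = 18 positive.
- Pairs with baseline: 15 + 18 = 33, hence 33 × 2 = 66 throat isolates.
- Nasal isolates: 0.45 × 66 = 29.7, rounded to 30.
- Total: 66 + 30 = 96, which is the stated figure.

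The number of breakthrough throat isolates to be classified is therefore 33. These are isolates, not children, since one child can contribute at both Day 7 and Day 28.

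**Step 2. Follow a strain from an unsampled site through the rule.**

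| Strain reaching the throat from the child's own unsampled site | Label under the plan | Correct? |
|---|---|---|
| Same as the baseline throat isolate | Original throat strain | Yes: a baseline strain |
| Same as the baseline nasal isolate | Baseline nasal strain | Yes: a baseline strain |
| Different from both | New, acquired | No: already carried by the child |

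Only the third row is in error. The documents make it plausible. The Supportive Preliminary Data section says that colonizing strains within one person often differ, even when typed by less discriminating methods. Aim 3 itself warns that nasal and throat isolates taken together are not always identical. The intervention also leaves skin and groin untreated.

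**Step 3. Size.**

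The quantity needed is the share *s* of breakthrough isolates that come from an unsampled own site and differ from both baseline isolates. The documents do not give it, so it is varied here as an assumption. Mislabelled isolates = 33 × *s*.

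| Assumed *s* | Mislabelled of 33 |
|---|---|
| 0% | 0 |
| 5% | 1.65 (about 2) |
| 10% | 3.3 |
| 20% | 6.6 (about 7) |
| 30% | 9.9 |

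No power or error-rate calculation enters, because the plan declares these analyses descriptive.

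**The case against.** The best defence is that the plan already discloses the gap. The Limitations section comes directly after the endogenous/exogenous sentence, names the untested sites, concedes that they can reseed the throat, and explains why they are not swabbed. The comparison rule is explicit, so a careful reader can work out what new means in practice. The aim is descriptive and no decision threshold hangs on the label. A match to a baseline isolate is also real evidence of endogenous origin, so the source claim is not empty.

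All of this stands, and it sets the scale of the point. It does not remove it: the Limitations text justifies the missing swabs but never says what they do to the label, and the sentence in Aim 3 is left unqualified.

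Some stronger readings are tempting but are not supported:

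- *Any strain from the child's groin or skin will be reported as acquired.* Only one that differs from both baseline isolates will be.
- *About a fifth of carriers would be missed.* The group's earlier cohort was "cultured at the anterior nares, oropharynx, and inguinal region". Carriage at any site was (137 + 405)/(350 + 812) = 542/1162 = 46.6%. Nares or throat carriage was 24% + 26% − 0.5 × 26% = 37%. The remainder is 9.6% of people, or 9.6/46.6 = 21% of carriers. With 45% overlap in place of 50%, the share is 18%. But these people are throat-negative, and every randomized child is throat-positive. The figure shows that unsampled carriage exists; it does not estimate *s*.
- *One misassigned child moves hypothesis (b) by a third.* The 3 is a net change, 18 − 15. Hypothesis (b) concerns all children cleared at Day 7 and positive at Day 28. That gross count is not given, and it exceeds 3 if any Day 7 positive child is negative at Day 28.
- *The label would steer the next trial away from body decolonization.* The Structured Abstract and the Hypothesis(es) and Aims section already include skin or body agents in that trial.
- *Only one isolate per swab will be typed.* The count of 66 is a planning estimate, and no colony-picking rule is stated.

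**Conclusion.** The point holds in a limited form. The plan attributes to the sequencing an ability that its two-site sampling does not provide: a non-match to both baseline isolates cannot establish exogenous acquisition. The error falls only on non-matching isolates; a match still supports endogenous origin. Its size cannot be derived from the documents. At an assumed 5% to 20% of the 33 expected breakthrough isolates it is about 2 to 7, and it could be none. This rests on the plan's own expected counts and on the sampling staying as described. The consequence is confined to how Aim 3 and its hypotheses (a) and (b) are interpreted. The primary endpoint, the sample size and the error rates are unaffected. The change is worth making because it corrects a stated conclusion at almost no cost.

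**What to change.** 1. In the opening text of Aim 3 (third category) and in item 1 of the list in Data Analyses, relabel the category as *not detected in nares or throat at baseline; source undetermined*.
2. Limit the endogenous/exogenous sentence: a match to a baseline nasal or throat isolate supports endogenous origin, while a non-match does not establish exogenous acquisition. Refer there to the untested sites named in Limitations. The sentence need not be deleted.
3. Reword hypotheses (a) and (b) in terms of strains *detected* or *not detected at baseline in the sampled sites*.

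The cost is protocol wording and a narrower Aim 3 conclusion. No added swabs, sequencing or participants are required, and the aim remains descriptive.
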